Questionnaires and child assessments are administered verbally in Kinyarwanda. Data are entered into SurveyCTO directly on Android tablets by trained independent local enumerators blinded to intervention status. Once the data are initially processed and de-identified, they are uploaded to a secure, password-protected Box folder. The data are further backed up to a secure server at Boston College.

Database

Data collection includes the collection of quantitative data regarding intervention effectiveness, dissemination and implementation (D&I) data regarding key domains of implementation science (e.g. acceptability, appropriateness, feasibility), qualitative data via face-to-face key informant interviews, and fidelity data collected throughout intervention delivery.

Quantitative study data and D&I survey data are collected using SurveyCTO, a secure mobile data collection platform that can be used offline. The SurveyCTO mobile application, referred to as SurveyCTO Collect, allows an enumerator to collect participant data using a password protected mobile phone or tablet, which is then uploaded to the secure SurveyCTO server. SurveyCTO has a built-in data monitoring and visualization tool that allows Field Coordinators

and Field Supervisors, who are based in the field during data collection, to monitor the uploading of study data as well as any inconsistencies in the data. Data will be regularly uploaded from tablets to the password protected SurveyCTO cloud-based server. Whenever form data is transmitted via a 3G or other internet network, it is encrypted in transit.

Qualitative key informant interviews are collected from primary caregivers (SM beneficiaries), CBVs, local and national government officials and other ECD and nutrition stakeholders such as International and local nonprofit organization and and international funding agencies. The aim of these interviews is to identify best practices and quality of early childhood and nutrition services delivery in Rwanda. A semi-structured interview guide is used to guide the qualitative interviews.

D. Data Analysis

Primary Outcomes

See Measures section for detailed information about the variables.

The table below outlines study primary predictors, control variables and moderators (possibly mediators if relevant).

	Questionnaire / Scale
PRIMARY PREDICTOR VARIABLES	
Treatment status [Treatment vs. Not]	
OTHER PREDICTOR VARIABLES [design variables]	
Cluster	
VUP-status [classic public works vs. expanded public works]	Government records
OUTCOME VARIABLES	
Malawi Developmental Assessment Tool (MDAT)	
Gross motor [standardized score]	MDAT
Fine motor [standardized score]	MDAT
Language [standardized score]	MDAT
Social [standardized score]	MDAT
Ages and Stages Questionnaire (ASQ-3)	
Gross motor [delayed/not delayed]	ASQ-3
Fine motor [delayed/not delayed]	ASQ-3
Communication [delayed/not delayed]	ASQ-3

Personal social [delayed/not delayed]	ASQ-3
Problem solving [delayed/not delayed]	ASQ-3
Anthropometrics	
Height-for-age (HAZ)	Anthropometrics
Weight-for-age (WAZ)	Anthropometrics
Weight-for-height (WHZ)	Anthropometrics
Middle upper arm circumference (MUAC)	Anthropometrics
"Father engagement "	
" father spends time every day caring for the child"	HOME
Family Violence	
Violent discipline [cumulative score, 0-7]	MICS-5 Hash discipline module
Intimate partner violence	
Victimization physical and sexual abuse past 3 months [cumulative score 0-7]*	Conflict Tactics Scale- CTS2
Perpetration physical and sexual abuse past 3 months [cumulative score 0-7]**	Conflict Tactics Scale- CTS2

*Among cohabitating or married mothers only

**Among cohabitating or married fathers only

***Among cohabitating or married caregivers only

Table 2. Study predictor and outcome variables.

Data Analysis Plan

Standard descriptive statistics will be used to describe the study sample. Frequencies and percentages will be reported for categorical variables and mean, median, standard deviation, interquartile range, maximum and minimum values will be reported for continuous variables. Anthropometric data will be cleaned for extreme out-of-range values. Scales will be created from individual items according to scoring instructions for each scale. All scales will be evaluated for psychometric properties. Visual inspection of histograms and other plots will be used to identify outliers.

Continuous Outcomes MDAT, WAZ, MUAC, WHZ: The goal is to determine the efficacy of SM at 12 months from study initiation. Measurements of all outcome variables (see Table 2 and Section B), are taken at baseline, midline (4 months post baseline), and endline (12 months post midline). Subjects are randomized (Section B) into a treatment group (SM) and CG. Effectiveness will be determined if the slope of the response variable for the SM group is significantly different than the slope of the CG group. To test this hypothesis, we will fit a linear

mixed effect model with a MDAT subscale, for example, as the response variable and the primary predictors are treatment group (SM vs CG), time and their two-way interaction included as fixed effects. Mixed effect models also known as hierarchical linear models (HLM) or multi-level models are a flexible tool for analyzing associations and changes over time in longitudinal studies when there are clusters of correlated data in the outcome variable. This design has three levels of nesting, families are measured within measurement waves, and measurement waves are nested within randomization cluster or region. Since, we expect region and time level effects subject-specific slopes and intercepts will be modeled as random effects nested within randomization cluster also modeled as a random effect. Additionally, there may be due to VUP program (recall we stratify the randomization of clusters within public works cluster). Type of VUP program will be model as a fixed effect. A mathematical representation of this model is:

$$Y_{ijkm} = B_0 + b_{0i} + B_1 * TreatmentGroup + B_2 * Time + b_{1i} * Time + B_3 * Time * Treatment group + b_{2k} + b_{3k} * time + B_{4m} * PubicWorksGroup + e$$

Where, Y_{ijkm} represents the value of the i th family ($i = 1 \dots I$), at the j th time point ($j=1, \dots 3$), in the k th cluster ($k = 1, \dots 200$) and m is the VUP indicator with levels expanded public works, classic public works and mixed. The set of b_{0i} variables represent subject-specific intercepts and are assumed $b_{0i} \sim N(0, \sigma_i)$. The b_{1i} are subject specific slopes and assumed $b_{1i} \sim N(0, \sigma_{slopes})$, the b_{2k} are randomization cluster intercepts and assumed $b_{2k} \sim N(0, \sigma_{region})$ and the b_{3k} are region specific slopes and assumed $b_{3k} \sim N(0, \sigma_{sregion})$. The value e represents residual variation and is assumed $e \sim N(0, \sigma)$. Efficacy will be based on the likelihood ratio test for inclusion of the Time*Treatment interaction (null hypothesis $B_3 = 0$). Random effects will be subject to a limited amount of model building as we would like to simplify the model where appropriate. For example, we would want to test if we can assume a common cluster slope versus a unique slope for each cluster. Cluster and subject-specific effects will be dropped from the model based on a Likelihood Ratio Test (LRT) for their inclusion. The estimation procedure while model building random effects will be Restricted Maximum Likelihood (REML). The primary hypothesis test which is based on the inclusion of a fixed effect will require models estimated by maximum likelihood. Because of randomization we have controlled in theory for all variables observed and unobserved, however treatment group imbalance may still be present. We explore treatment group characteristics for in-balance. However, previous work has showed baseline differences to be minimal.

Model assumptions and alternative tactics: Model assumptions will be verified. In particular we will examine the distributions of the residuals to verify that normality assumptions hold. Residual plots will reveal violations of the normality assumptions. Panel plots will be examined to look at functional shape assumptions within subject. In the case of non-normality of outcomes, we will consider response transformations or the use of models that do not require the normality assumptions including the class of generalized linear mixed effect models. If the linearity

assumption does not hold across time (baseline, 3 months, and 12 months) we can treat time as a categorical variable to examine differences between the treatment groups at individual time points focusing on the 12-month group differences adjusted for baseline. If examination of panel plots reveals a large amount of heterogeneity among trajectories of the outcomes by subjects we can use Growth Mixture Models which first identify clusters of similar trajectories from which we can test for treatment group differences in terms of membership in the clusters of similar trajectories.

Outliers will be flagged through visual inspection and standardized residual values greater than 3. A sensitivity analysis will be done to determine if outlier removal changes the coefficient values. If we find that outliers are having an oversized effect on the estimated coefficient values we will give preference to the models where the outliers are removed. However, we will present both results.

Some responses are scales or derivations of scales in particular the MDAT and the ASQ. We will examine the psychometric performance of these scales. We are especially concerned with internal consistency and item reliability. If these scales do not show at a minimal amount of internal consistency (Cronbach's Alpha > 0.6) these items will not be considered for analysis. If particular items are an issue they may be dropped from the scale. Research, in areas like Rwanda suffer because standard scales have not been validated on these populations.

Binary Outcome ASQ, shared decision making, father engagement: The analysis for these outcomes will be similar to the analyses above with accommodations being made for the fact the ASQ is a binary outcome. In particular, we will have to make use of mixed effect logistic regression models a form of generalized linear mixed models (GLMM) with a binomial distribution and a logistic link. Outside of accounting for the correct distribution of the response variable the analysis will follow the methods outlined in the previous MDAT section.

Model Assumptions and Alternative Tactics: We will examine Pearson residuals to assess goodness of fit. Alternative methods include the use of quasi-binomial mixed effects regression (in the case of over dispersion). However, such models do not have a full likelihood and instead of LRT test we will have to rely on the Wald-type type test for regression coefficients.

In fitting logistic mixed effect regression models, it is possible that we may run into numerical difficulties in computing a likelihood ratio test, so score type tests may be needed. This is more likely to occur in the case of testing for variance components.

Count Outcomes, harsh discipline, physical and sexual violence: These metrics count types of harsh discipline action or physical and sexual abuse as suffered or inflicted. Our experience with these scales is that there are more values of zero than what would be predicted by a standard

Poisson distribution. Our analysis will make use of Zero Inflated Poisson (ZIP) models (Everitt, & Hothorn, 2005; Long, 1997). These models belong to the more general class of mixture models. In particular they model the binomial probability of a count of zero versus a count greater than zero and the Poisson probability for counts greater than zero. In particular we will fit mixed effect models as described in the continuous variable sections but under the ZIP distribution assumption.

A key difference between a mixture model and more standard probability distributions is the fixed effects structure and tests for significance can vary between the two parts (binomial and Poisson). Likelihood ratio testing for the Time*Treatment group interaction will be performed for both components of the mixture model. A significant result of the LRT test for the binomial portion would indicate that the probability of no violence (inflicted or suffered) differed between the treatment groups. A significant result of the LRT on the Poisson portion of the ZIP model would indicate that among those who inflicted or suffered harsh discipline or violence the mean amount of violence differed between the treatment groups. The two portions are contained in a single likelihood function and parameter estimation is done simultaneously.

Model Assumptions and Alternative Tactics: The key assumption in these models is the ZIP distribution of the response variables. We will visually inspect the distribution of the outcome variables to verify that we are fitting the correct model. Alternative distributions could be Poisson, Quasi-Poisson, Binomial (data dichotomized due to lack of variability), or Negative Binomial. These are non-mixture models and modeling will follow the process outlined in the continuous outcomes section.

Secondary Outcomes: Stunting measured by Height-for-Age is an important outcome. However, we do not expect to see significant changes in this variable in the 12-month timespan. We do expect to see a reduction in stunting even if it does not achieve statistical significance. Using the models described in data analysis plan we can extract the coefficient for the time by treatment group interaction as an estimate of the size of the effect of SM on stunting. Effect sizes of other secondary outcomes will be reported similarly.

Missing Data

We will apply the ITT principle to all of our analyses. Unless a subject dies, the ITT convention is to keep them in the study; HLM handles this well since the linearity assumption allows us to estimate subject-specific parameters so long as we have at least two data points. The method of mitigating bias due to missingness known as full-information maximum likelihood estimation (FIMLE) can be problematic in mixed effects linear models. Principled methods of multiple imputation such as chained equations will be employed.

Power and Sample Size

Assuming the linear mixed effect model described above. The following values were used to calculate statistical power. We assumed a total of 200 clusters with 5 families per cluster. We assume a linear relationship over time. The significance level is set at 0.05. The statistical test was the likelihood ratio test for the inclusion of the time by treatment group interaction. The ICC was set at 0.10. A variable for public works type which was categorical with 3 levels was included in the model. Within public works type a ratio 1:1:2 for expanded:both:classic was assumed. Variability was set to one so that effect sizes may interpreted as “Cohen-Like” effect sizes. We found that we have at least 90% power to detect an effect size of 0.25 and at least 80% power to detect an effect size of 0.22. GLIMMSE software was used for these calculations.

E. Safety & Adverse Events

Risks to Subjects

The following risks were identified and submitted to the Boston College IRB:

1. Participation in the intervention may lead adults to confront stressful personal or family issues or generate concern about social harm resulting from loss of confidentiality, which may elicit distress in some participants.
2. In some cases, fatigue from the psychosocial assessment administered pre/post-intervention and at 12-months follow-up may occur.
3. There is a small risk of loss of confidentiality.
4. Participation in the intervention may create issues within the community if a household receiving the SM intervention is viewed as receiving additional services or monetary support.

We consider most risks associated with participation in the study to be unlikely. Two previous pilots of SM have been carried out with vulnerable families in Rwanda. Previous study iterations have demonstrated that processes related to confidentiality are upheld throughout the entire study. Further, no participants have indicated distress or fatigue with the assessments. Weekly field reports from the Laterite enumerators have not indicated any issue with the assessments, length of time to administer, issues with confidentiality, or distress caused.

There are other risks we consider to be likely: intimate partner violence in the home and tensions with neighbors due to participation in the intervention. The CBVs have received comprehensive training on recognizing intimate partner violence in the home as well as how to activate our risk of harm protocol to ensure we assess the harm and make the necessary referrals. The other risk related to community tensions due to participation have resulted in several study changes. First, in the event that an issue arises with a neighbor, the CBV immediately alerts their supervisor and the village leader or elder to better understand the source of the issue. During this time, the intervention is paused. The family is then given the option to conduct the intervention

offsite at the local government offices at the cell level. As a preemptive measure, all supervisors have traveled to the field to meet with the village leader and Cell official to further communicate the SM as a coaching intervention and not an intervention where goods or money are provided to families.

Monitoring

A Risk of Harm decision tree, along with flagged questions from the assessment battery, provides a structured protocol for monitoring and responding to adverse effects on participants. Interventionist supervisors have daily phone check-ins with the interventionists as well as weekly face-to-face meetings. These check-ins provide an opportunity for monitoring families in the study and ensuring all study risks are addressed appropriately. Further, these check-ins allow the supervisor to anticipate any potential risks and work with the interventionist to initiate support or a referral to mitigate any potential risks.

Stopping Procedures if relevant.

The intervention will be paused or stopped if a participant is experiencing active psychosis or is experiencing harm as a result of participation in the intervention. While these instances are expected to be rare, formal procedures are in place. If an adverse event or risk of harm is detected, a study supervisor works with the CBV to collect as much information on the issue, and then conducts an in-person assessment of the situation. Depending on the case, this assessment may include discussion with local CHWs and village leaders to gain further information about the participant or family.

F. Study Limitations

A primary study limitation is the reliance on caregiver-reported measures, which could suffer from differential bias because parents who are exposed to the intervention may be more knowledgeable about or more pressured to provide a socially desirable answer. However, the quality monitoring approaches utilized by study enumerators (described in detail above) provide important checks for ensuring the data are collected as intended and that enumerators are not engaging in any sort of behaviors to coerce specific answers from caregivers. A second study limitation regards the reliance on western created measures to assess primary and secondary study outcomes. Extensive work was done to refine and adapt measures to fit the Rwandan context with assessment questions forward and back translated into Kinyarwanda following best practices (Van Ommeren et al., 1999) through two pilot studies (Betancourt et al. 2017 and other forthcoming manuscripts). Further, psychometric analysis of study measures assessing primary and secondary study outcomes indicate strong reliability and validity.

G. Compensation

Incentivization of CBVs

CBVs receive several types of incentives given their role in delivering SM. The incentive rate was established based on learning from what other similar programs require for a volunteer coach as well as considerations regarding the CBV scope of work. Calculated at a per household rate, CBVs will receive 1,200 Rwandan Francs each week per household in their caseload to cover cell phone airtime, transportation, and the family visit. CBVs also receive 2,000 Rwandan Francs to cover transportation for weekly peer support groups over the course of 12 weeks. To cover their participation in a three-week intensive training, CBVs receive an additional 75,000 Rwandan Francs. Non-monetary incentives include an umbrella, branded t-shirt, mobile phone, lockbox for sensitive materials (intervention manual, intervention workbook, notes from supervision), rain boots, a branded bag, a branded identification badge, and materials needed to deliver the intervention.

Incentivization of Household Beneficiaries

Household beneficiaries will receive 5000 Rwandan Francs for each timepoint of data collection (baseline, post-intervention, and 12-months follow-up). Households selected to participate in qualitative interviews will receive an additional 3000 Rwandan Francs for each qualitative interview. Households selected to participate in the D&I measures will receive an additional 3000 Rwandan Francs for each time point (pre- and post-intervention). Families are reimbursed in cash once they have completed the assessment or interview.

H. Provisions for vulnerable subjects

All household beneficiaries in the study have an Ubudehe 1 poverty categorization. As such, all study procedures are created and implemented with provisions for vulnerable participants. Specifically, risk of harm/adverse event procedures are in place to identify any risk of harm situations related or not related to participation in the study. Further, funds are available if any participant requires a referral or transfer to a higher level of care, such as transport to and treatment at a district hospital, for example.

I. Data archiving and dissemination

Results from the trial will be published in peer-reviewed journal articles and presented at high level conferences. A formal dissemination event involving study funders and stakeholders will be held in Kigali, Rwanda. Study quantitative data will also be uploaded to the World Bank Microdata Catalog as part of study funding deliverables.

References

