Eighty-seven percent of children less than 6 months old are breastfed but stunting rates rise from 18% at 6–8 months of age to 38% at 18–23 months of age and up to 49% in the lowest poverty quintile. Dietary diversity is limited in Rwanda, especially amongst poor children. In the early years, the need for nutrients to fuel brain development and physical growth is particularly high. A UNICEF/Rwanda Ministry of Health study found that a very limited diet for children—in terms of variety and nutritional content—is common in Rwanda, due both to poverty and poor feeding practices. The study found that a high percentage of children in the poorest households did not receive three meals a day and only 17% of children aged 6–23 months have a minimally acceptable diet. In addition, early childhood development knowledge, attitudes and practices of Rwandan parents are limited. A 2014 UNICEF study found that only 12% of primary caregivers for 2–3-year-old children engaged in three or more activities to promote learning or school readiness (e.g., singing songs, telling stories, teaching the child something new or looking at

pictures in books and magazines with the child). The ECD problem is compounded by the fact that violent discipline is prevalent. An Early Childhood Development and Family Services UNICEF baseline evaluation in 20 sites in Rwanda showed that 19.8% of children 0–11 months old and 80.7% of children 24–36 months old are exposed to some form of violent discipline; 34.4% of caregivers believe that physical punishment is necessary to raise a child well. In addition, men are often not significantly involved in supporting children’s early development and decision making is not equally shared by men and women.

Specific Aims

The proposed study will investigate the effectiveness of Sugira Muryango, a family home-visiting caregiver coaching model intended to promote child development, healthy caregiver-child interactions and reduce caregivers’ use of harsh punishment among families living in extreme poverty in Rwanda.

The study’s Specific Aims are:

Aim 1. To test the effectiveness of Sugira Muryango in promoting child development (cognitive, socio-emotional, language and physical development), reducing harsh punishment and increasing father engagement in childcare in poverty-affected households participating in a social protection program (the VUP program):

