Family inclusion criteria are (a) living in the Rubavu, Ngoma or Nyanza District of Rwanda. Inclusion criteria for families are: (b) being VUP-eligible (according to the Rwandan government), (c) having at least one child aged 6–36 months living in the home, and (d) having at least one caregiver who is willing to discuss and enhance their caregiving practices by interacting with a home-visiting coach (CBV).

Further caregiver inclusion criteria are: (a) is aged 18 or older and cares for child(ren) and (b) lives in the same household as child(ren). We will enroll both single and dual caregiver families

to reflect population dynamics. Legal guardians may be parents, aunts, uncles, grandparents, or foster parents.

Family exclusion criteria are not meeting inclusion criteria, caregiver having severe cognitive impairments which preclude their ability to speak to the research questions under study, or families or caregivers are in the midst of crisis (e.g., a caregiver with active suicidal attempts or psychosis). Families with ongoing crisis or disability will be referred to appropriate services.

Consent Procedures

During household enrollment, Laterite – the local data collection subcontractor - uses VUP lists to go door to door to assess household eligibility and offer participation in the SM home visiting intervention. If a household is eligible and wants to enroll, the field team consents the primary and secondary caregivers and the VUP head of household if different from the primary and secondary caregiver. The primary caregiver also provides consent for the child ages 6–36 months. If a caregiver is absent, the team make a plan to come back either later in the day or the next day. The field team gives each home a week for this to be completed before replacing the home. Given that most Ubudehe 1 individuals (those eligible for VUP public works) are illiterate, the consents are orally communicated to the caregivers. The caregivers either sign their name or make a mark (thumbprint) on the consent form. The Laterite field team carries additional copies of the consent in case the family would like to keep a copy. The consent forms are stored in a portable lock box until they are transferred to Kigali and stored in locking file cabinets at the FXB-Rwanda office. Study participants are re-consented prior to each follow-up data collection timepoint.

[figure not shown]
Randomization Plan

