Household treatment status is considered the main predictor of all outcomes.

Public Works program

The household’s public work (VUP) status is considered an important design-variable.

Child anthropometrics

Children’s physical growth status is used as a proxy for their nutritional status and assessed using measures of standardized height-for-age (HAZ), standardized weight-for-age (WAZ), standardized weight-for-height (WHZ), and middle upper arm circumference (MUAC). Height is measured in centimeters to the nearest 0.1 cm. Weight is measured in kilograms to the nearest 1 gram. Middle upper arm circumference is measured in centimeters to the nearest 0.1 cm. Standardization is done using software provided by the World Health Organization. Outcomes related to children’s HAZ, WAZ, WHZ and MUAC are treated as continuous.

Malawi Developmental Assessment Tool

Child development across domain of gross motor, fine motor, language and socio-emotional development is assessed using the Malawi Developmental Assessment Tool (MDAT) tool.

MDAT was developed for use in Malawi with the aim to develop a culturally appropriate tool for use in rural Africa (Gladstone et al. 2010). MDAT is an observational task-based assessment where a trained rater assesses the child's ability to perform different tasks. The MDAT has been tested in several African countries where it has shown good reliability and validity. We calculate a standardized continuous score for each domain Fine motor, Gross motor, Language, and Socioemotional using standardizations provided by the MDAT team.

Ages and Stages Questionnaire

The Ages and Stages Questionnaire 3 (ASQ-3) uses a series of parent-completed questionnaires that are designed to screen the developmental performance of children in the areas of gross motor skills, fine motor skills, communication, and problem solving (Squires & Bricker, 2009). We administer the ASQ-3 through oral interviews with the caregiver who states that they know the child best ("the primary caregiver"). The ASQ-3 is scored using standard guidelines for standardization resulting in create binary outcome variables for each domain indicating whether or not the child showed "developmental delay" vs. "no developmental delay".

Violent discipline

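### Violent discipline is an unstandardised count modelled without child age, although the protocol's own background shows a steep age gradient; prespecifying age and age-by-time would recover a modest amount of precision

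*Combined protocol and SAP*

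**What the plan says.** - **Model terms.** Under Data Analysis Plan (continuous outcomes), "the primary predictors are treatment group (SM vs CG), time and their two-way interaction included as fixed effects". One more fixed effect follows: "Type of VUP program will be model as a fixed effect". The rest are random intercepts and slopes for subject and cluster. Efficacy is the likelihood ratio test of the time-by-treatment term.
- **Covariates.** The text before Table 2 says "The table below outlines study primary predictors, control variables and moderators", but the table lists only treatment, cluster and VUP status as predictors. Child age is not there.
- **Count outcomes.** Harsh discipline and partner violence use the same structure under a ZIP distribution, because "Our experience with these scales is that there are more values of zero than what would be predicted by a standard" Poisson model. Table 2 defines violent discipline as a cumulative score from 0 to 7, with no standardisation for age.
- **Age.** Eligibility requires "having at least one child aged 6–36 months living in the home". The Background cites a survey at 20 sites in which "19.8% of children 0–11 months old and 80.7% of children 24–36 months old are exposed to some form of violent discipline".
- **Other child outcomes.** MDAT, ASQ-3, HAZ, WAZ and WHZ are described as standardised. For MUAC the plan says "Middle upper arm circumference is measured in centimeters to the nearest 0.1 cm"; its scale for analysis is not clearly stated.

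**The concern.** The test compares slopes, so what matters is whether expected change depends on age. If the survey gradient resembles the trial's, a child enrolled at 6 months moves through the steep part of the curve during follow-up, whereas a child enrolled at 30 months or older may already be near the top. With no age term, that predictable variation is treated as noise, and a chance difference in age between arms feeds into the treatment estimate. Age mixing may also produce some of the zeros that motivate ZIP, since the survey figures imply 80.2% unexposed in the youngest band against 19.3% in the oldest. Age is needed for eligibility and for the z-scores, so nothing new has to be collected. If it is not prespecified, a later age adjustment would be post hoc: the plan says it will look for imbalance but names no adjustment.

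**Working it through.** **1. The plan's power figure.** Inputs from Power and Sample Size: 200 clusters of 5, ICC 0.10, SD 1, alpha 0.05 (two-sided assumed). Design effect = 1 + 4 × 0.10 = 1.4; effective n per arm = 500/1.4 = 357.1. Power = 0.916 at effect 0.25 and 0.836 at 0.22, in line with the stated minimums of 90% and 80%.

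**2. Age curve (assumed).** Entry ages uniform over 6-36 months; prevalence linear or logistic between the band midpoints (5.5 and 30 months), then flat at 80.7%. The linear slope is (0.807 − 0.198)/24.5 = 0.0249 per month. From baseline to endline is 4 + 12 = 16 months. Expected change for a child enrolled at 6 months is 16 × 0.0249 = 0.40 (0.42 on the logistic curve); at 30 months or older it is 0.

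**3. Share of change variance explained by age.** R² = Var(d)/(Var(d) + W). Here d is the expected change at a given age, and W is the mean over age of p₀(1−p₀) + p₁(1−p₁) − 2ρ√[p₀(1−p₀)p₁(1−p₁)], with ρ the within-child correlation given age, taken as 0 to 0.4. For the linear curve and ρ = 0:

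- d is 0.398 from 6 to 14 months, falls linearly to 0 at 30 months and stays there. Mean d = 0.212, mean d² = 0.0704, so Var(d) = 0.0253.
- W = 0.207 + 0.169 = 0.376.
- R² = 0.0253/0.401 = 0.063.

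Across both curves and ρ up to 0.4:

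| Scenario | R² of change |
|---|---|
| 16 months, plateau | 6-12% |
| 12 months, plateau | 4-7% |
| 16 months, linear curve continuing up to 100% | 4-6% |

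**4. Value in families.** For independent children the equivalent is 1/(1 − R²), or 7-13% more families in the first scenario. The trial is clustered, and age varies mainly within clusters, so only the within-cluster part shrinks. Applying the plan's ICC to the change, the variance of a cluster mean is 0.10 + 0.90/5 = 0.28, and after adjustment 0.28 − R²/5:

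- R² = 0.063: 0.28/0.2674 = 1.05. R² = 0.115: 0.28/0.257 = 1.09. So **5-9%**, or 50-90 families on 1,000.
- 12 months: 3-6%. Without the plateau at 16 months: 3-5%.
- Standard error falls by 1 − 1/√1.05 to 1 − 1/√1.09, about 2-4%. Applied to the generic power calculation, power at 0.22 goes from 0.84 to 0.85-0.87.

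**5. Which term matters.** Four data sets of 200 × 5 children at 0, 4 and 16 months were simulated and fitted by maximum likelihood with child random intercept and slope (cluster effects left out of the fit). Adding an age main effect left the time-by-treatment estimate identical to five decimals and cut its SE by 0-1.3%. Adding age-by-time cut the SE by about 2-5% (for example 0.03588 to 0.03529, and 0.03528 to 0.03359) and moved the estimate by up to 0.020 (0.03908 to 0.01928), which is the correction for chance imbalance.

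**6. Sensitivity.** In a larger simulation of the slope contrast with linear and quadratic age, variance ratios were 0.93 and 0.89 with the plateau, and 0.90 and 0.79 if prevalence fell to 50% by 52 months. Cluster effects there were constant over time and so cancel from the slope; the ratios make no allowance for clustering of change. For the fallback, endline adjusted for baseline, the ratio was 0.89-1.01.

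**The case against.** - **The gradient is not the trial's.** It comes from an outside survey of any exposure, not a 0-7 count, and its youngest band includes infants under 6 months, who are not enrolled. On the linear curve a child of 8.5 months has prevalence 0.198 + 3 × 0.0249 = 0.273, so about 73% zeros rather than 80%. This stands, and is why the size is a range. It does not remove the case for an age term, since the protocol offers no contrary evidence.
- **Each child is its own control.** True for an age main effect, as step 5 shows. It does not answer age-dependent change. Random slopes accommodate such differences but count them as unexplained variation.
- **A reader might infer that every model loses precision.** The documents do not support that. MDAT, ASQ-3, HAZ, WAZ and WHZ are already standardised. No age gradient is given for father engagement, so it is not part of this point. None is given for MUAC either, and its analysis scale is unclear, so that part is conditional.
- **A reader might infer a larger gain from the contrast between 20% and 81%.** Age band explains 21-36% of variance at enrolment, depending on the missing middle band, but the planned test is on change. By 16 months enrolled children are about 22-52 months old, and age explained only 2-4% of endline variance in the simulation.
- **It is not quite free.** There are several extra terms, twice over in ZIP, in models for which the plan already expects possible numerical difficulty. In logistic and ZIP models the treatment effect becomes conditional on age. Both stand as small costs; those effects are already conditional on random effects.

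**Conclusion.** The point holds for violent discipline, and conditionally for MUAC. The plan leaves out a covariate that its own background marks as strongly related to the outcome, in a model where expected change very likely depends on it. The gain is modest: 6-12% of change variance over 16 months with a plateau at 80.7%, worth roughly 5-9% more families, and 3-6% over 12 months or 3-5% at 16 months without the plateau. This rests on uniform entry ages, an assumed curve between the two survey figures, within-child correlation of 0 to 0.4, the plan's ICC applied to change, and age varying mainly within clusters. It was worked out for a binary outcome on a linear scale; nobody can read a figure for ZIP on the 0-7 count from it.

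A reader might infer that the treatment estimate is biased, or that ZIP is the wrong model. Neither follows. Allocation is randomised, so an age difference between arms is chance. Age may account for some zeros, but the documents do not show that it accounts for the excess.

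**What to change.** In the violent discipline model, prespecify baseline child age (linear plus quadratic, or a spline) and its interaction with time as fixed effects, in both the zero and the count part if ZIP is kept. State that the treatment effect is then conditional on age. Keep the time-by-treatment test as planned, and name a simpler form (age and age-by-time, linear only) to use if the full model does not converge.

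State the scale on which MUAC is analysed. If it is raw centimetres, use the same age terms or an age-standardised score. Father engagement and the standardised outcomes need no change on this ground. List age among the control variables in Table 2.

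Cost: no new data. Linear and quadratic age, each with its time interaction, makes four terms, or eight across the two ZIP parts.
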